# 4.2. Study objectives

## **Primary Objectives**

- 1. To estimate VE after 2 doses of RZV for preventing HZ in participants ≥50 YOA with SLE.
- 2. To estimate VE after 2 doses of RZV for preventing HZ in participants ≥50 YOA with MS
- 3. To estimate VE after 2 doses of RZV for preventing HZ in participants ≥50 YOA with RA.
- 4. To estimate VE after 2 doses of RZV for preventing HZ in participants ≥50 YOA with IBD
- 5. To estimate VE after 2 doses of RZV for preventing HZ in participants ≥50 YOA with PsO
- 6. To estimate VE after 2 doses of RZV for preventing HZ in participants ≥50 YOA with PsA

219111 (EPI-ZOSTER-097 VE US DB)
Protocol Final

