- 4. Secular or seasonal trends in RZV use: RZV vaccination patterns may have changed during the COVID-19 pandemic. Receipt of RZV will be accurately captured in the OptumTM database, including dates of administration such that receipt of dose 1 and dose 2 are correctly ascertained. In addition, the study methods will ensure similar distributions by calendar year and season among vaccinated and unvaccinated participants and sensitivity analyses will be performed to assess if the occurrence of the COVID-19 pandemic resulted in an increase or decrease of VE. This will be further discussed in the SAP. Although in this study appropriate methodologies will be applied to statistically adjust for differences between RZV exposed participants versus RZV unexposed participants, not all potential confounders may be available in the database, and residual confounding may still be present.
- 5. Secular trends in medication use for AIDs: Newly approved therapies may be available for AIDs and may be used primarily for those with more severe disease initially. After a few years on the market, these therapies may be used in less severe disease or disease subsets. These trends may impact differences in populations and differences in the classification of disease occurrence. The study methods will ensure similar distributions by calendar year and season among vaccinated and unvaccinated participants.
- 6. Unmeasured confounding: Disease severity and disease duration may be associated with receipt of the vaccine and/or subsequent risk of HZ. However, these factors are challenging to measure in administrative claims data or may not be measured. This study assesses proxies for disease activity (such as medication use and healthcare use for disease severity) to measure confounding. Disease duration is difficult to measure as the entire medical history of a participant is not available. Confounding by indication is another potential limitation. Participants may receive RZV before initiating immunosuppressive (or more highly immunosuppressive) treatment in

219111 (EPI-ZOSTER-097 VE US DB)
Protocol Final

order to protect them from that planned treatment. This would bias the VE estimates. To address this bias, participants receiving JAK inhibitor, for example, one month after index date in the JAK inhibitor medication category will be included to account for this.

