#### 6.3. Covariates of interest

Age in 5-year increments: 50-54, 55-59, 60-64, 65-69, 70-74, 75-79, ≥80 [Harpaz, 2019; Hayter, 2012; Johnston, 2009; Kawai, 2016; Marra, 2020; Tsai, 2017; Yun, 2016; Wallin, 2019; Weng, 2007; Yamaguchi, 2021].

Sex: female/male [Hayter, 2012; Johnson, 2015; Kawai, 2016; Marra, 2020; Tsai, 2017; Yamaguchi, 2021]

Race/ethnicity: Asian, Black, Hispanic, White, Multiple/Other/Unknown [Kawai, 2017a]. The definition of race/ethnicity will be further discussed in the SAP.

Use of AID-related medications: includes but not limited to: tofacitinib, biologics and conventional synthetic DMARD combination therapy, biologics (tumor necrosis factoralpha blockers), and disease-modifying antirheumatic drugs in the 365 days prior to the index date, as detailed in Appendix 4[Baumrin, 2019; Chakravarty, 2013; Khan, 2018; ILai, 2021; Marra, 2016; Yamaguchi, 2021].

Medical encounters: number of inpatient admissions in the 365 days prior to the index date (continuous), number of ambulatory visits in the 365 days prior to the index date (continuous), number of Emergency Department visits in the 365 days prior to the index date (categorized 0, 1, 2-3,  $\geq$ 4), number of rheumatologist outpatient visits (for SLE, RA, PsA) in the 365 days prior to the index date, number of dermatologists outpatient visits

219111 (EPI-ZOSTER-097 VE US DB)
Protocol Final

(for SLE, PsO) in the 365 days prior to the index date, number of neurologist outpatient visits (for SLE, MS) in the 365 days prior to the index date.

Healthcare cost level: categorized according to specific ith percentile in the 365 days prior to the index date. The definition of healthcare cost level will be further discussed in the SAP. Participants followed during the observation period without any claims reported will be considered as having a cost of \$0; if a participant has a negative estimated cost, the cost will be set to missing and the cost of all the unvaccinated matched participants will be set to missing also.

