# 7.6. Matching

For the primary objectives, once sub-cohorts for each AID condition are identified, participants meeting inclusion criteria who receive 2 doses of RZV at least 28 days apart at the index date will be matched exactly with unvaccinated participants on age category by 5-year increments (50-54, 55-59, 60-64, 65-69, 70-74, 75-79, ≥80) and AID-related medication category (mutually exclusive) based on current use at the index date within the same AID group. Medication categories will be based on the medication windows described in 13.6. For the secondary objectives, participants meeting inclusion criteria who receive 1 dose of RZV at the index date will be matched with unvaccinated participants by 5-year increments (i.e., 50-54 age grouping) and by AID-related medication category (mutually exclusive) based on current use at the index date. Matching will be done with replacement.

Following matching as described above, propensity scores based on the likelihood of receiving RZV dose 2 versus no RZV vaccination will be calculated using logistic regression models with RZV vaccination as the dependent variable and independent variables as outlined in Section 6.2 to select the 3 unvaccinated participants which are the closest to each vaccinated participant, to reach a ratio of RZV vaccinated to RZV unvaccinated of 1:3. Propensity scores will be calculated within each cohort defined by AID to balance measured confounders (details to be provided in the SAP) among patients receiving RZV dose 2 and comparator patients with no prior RZV vaccination. A second cohort of patients will be created to compare patients receiving RZV dose 1 to patients with no prior vaccination, using the same approach to calculate propensity scores within each cohort defined by AID based on the likelihood of receiving RZV dose 1 versus no RZV vaccination. An unvaccinated patient may serve as a comparator for both the dose 1 and dose 2 cohorts, although separate index dates will be applied.

Covariate balance will be assessed before and after applying propensity scores using standardized mean differences, with standardized differences of 0.2 suggestive of important imbalance [Austin, 2009a; Austin, 2009b]. Any covariate demonstrating imbalance after weighting, suggesting residual confounding, will be included as an

219111 (EPI-ZOSTER-097 VE US DB)
Protocol Final

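### IBD is the only primary cohort for which Section 6.3 lists no specialist visit count, so gastroenterology contact is neither modelled nor balance-checked in its own right

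*Protocol*

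**What the plan says.** Protocol Section 4.2 sets six primary objectives, one per disease. The fourth is "To estimate VE after 2 doses of RZV for preventing HZ in participants ≥50 YOA with IBD".

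Section 6.2 points to Section 6.3 for the covariates to be included. Under medical encounters, Section 6.3 lists inpatient admissions, ambulatory visits and emergency department visits for everyone. It then adds specialist counts tied to named diseases: "number of rheumatologist outpatient visits (for SLE, RA, PsA) in the 365 days prior to the index date", a dermatologist count for SLE and PsO, and "number of neurologist outpatient visits (for SLE, MS) in the 365 days prior to the index date". There is no gastroenterologist count here or elsewhere in the protocol.

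Section 7.6 uses this list for the propensity score, through "logistic regression models with RZV vaccination as the dependent variable and independent variables as outlined in Section 6.2", fitted within each disease cohort. Covariates still imbalanced afterwards go into the Cox model.

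Section 5.2.1 explains why healthcare use matters. Severity and duration may relate to vaccination and to herpes zoster (HZ) risk and are hard to measure in claims. The plan's answer is: "This study assesses proxies for disease activity (such as medication use and healthcare use for disease severity) to measure confounding".

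**The concern.** The plan adds a disease-specific visit count to the all-cause ambulatory count for five of its six primary cohorts. The reasoning in Section 5.2.1 applies equally to IBD: contact with a gastroenterologist could plausibly relate both to being offered the vaccine and to disease activity and treatment intensity, and so to HZ risk.

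The safeguard in Section 7.6 would not reveal the gap. It can flag only covariates that are on the list. Gastroenterology contact could be imbalanced after matching without anyone seeing it, provided the total of ambulatory visits was balanced.

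The IBD estimates serve primary objective 4 and secondary objectives 1, 6 and 13, and contribute to objective 17. Section 11.3.1 puts RA and IBD first in the sequence of analyses, so the point is best settled before that work starts.

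**Working it through.** **Step 1. Coverage.** Setting the specialist counts of Section 6.3 against the six primary cohorts gives:

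| Cohort | Rheumatologist | Dermatologist | Neurologist | Number of counts |
|---|---|---|---|---|
| SLE | yes | yes | yes | 3 |
| MS | – | – | yes | 1 |
| RA | yes | – | – | 1 |
| PsO | – | yes | – | 1 |
| PsA | yes | – | – | 1 |
| IBD | – | – | – | 0 |

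**Step 2. Is the list meant to be open?** In Section 6.3 the medication item is expressly non-exhaustive, and the definitions of race/ethnicity and cost level are deferred to the SAP. The medical-encounters item carries neither qualification and names diseases for each specialty. Read as it stands, it leaves IBD out.

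**Step 3. Is the variable obtainable?** Section 3.1 says that medical claims carry provider specialty codes. The three listed specialist counts need the same information.

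**Step 4. Size, as an illustration only.** The documents give no prevalence, imbalance or HZ effect for gastroenterology contact. The values marked as assumed are not from the protocol.

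*Event count.* Table 2 gives 693 HZ cases in 51,090 person-years for unvaccinated IBD: 693 / 51,090 × 1,000 = 13.56 per 1,000, which reproduces the stated rate. Table 3 gives 5,865 two-dose IBD recipients with 1.4 years of average follow-up. The ratio is 1:3. Assume VE of 50% and equal follow-up in both groups.

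- Vaccinated: 5,865 × 1.4 × 13.56/1,000 × 0.5 = 55.7, about 56 events.
- Unvaccinated: 3 × 5,865 × 1.4 × 13.56/1,000 = 334 events.
- SE of log HR ≈ √(1/55.7 + 1/334) = 0.145.

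This ignores the reuse of controls under matching with replacement and any loss to the three-month follow-up rule. Either would enlarge the SE and make the shifts below a smaller fraction of it.

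*Imbalance.* Take a binary marker of high contact with prevalence 30% in one group and 39.5% in the other (assumed). The standardized difference is 0.095 / √[(0.30×0.70 + 0.395×0.605)/2] = 0.095 / 0.474 = 0.20, which is the level Section 7.6 treats as important.

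*Bias factor* = (1 + p₁(HR − 1)) / (1 + p₀(HR − 1)), with p₁ = 0.395 among vaccinated, p₀ = 0.30 among unvaccinated, HR the marker's effect on HZ (assumed 1.5 to 2), and no control through other covariates:

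- HR 1.5: 1.1975 / 1.150 = 1.041; ln 1.041 / 0.145 = 0.28 SE. A true VE of 50% would read 1 − 0.5 × 1.041 = 47.9%.
- HR 2: 1.395 / 1.300 = 1.073; ln 1.073 / 0.145 = 0.49 SE. A true VE of 50% would read 46.3%.

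If the unvaccinated have the higher prevalence, the factors invert (1/1.041 and 1/1.073) and the same VE would read about 52.0% and 53.4%.

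*A second set of assumed inputs* uses prevalence of 20 to 30% per group, differing by 5 to 10 points, and an HZ rate ratio of 1.3 to 2.0. The factors run from 1.2/1.3 = 0.92 to 1.3/1.2 = 1.08. A true VE of 50% would read between 45.8% and 53.8%, and a true VE of 70% between 67.5% and 72.3%.

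**The case against.** A reader might infer that IBD is adjusted less well overall than the other five cohorts, and that its residual confounding is therefore larger. The documents do not support either step.

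- IBD keeps the inpatient, ambulatory and emergency counts, cost level, comorbidities, preventive services and 365-day medication use. It is also matched exactly on "AID-related medication category (mutually exclusive) based on current use at the index date within the same AID group", and Section 5.1 matches UC to UC and CD to CD.
- Medication use is the other proxy named in Section 5.2.1. The IBD categories are defined (Section 13.6.2), while those for PsO and PsA are still to be generated (Sections 13.6.4.1 and 13.6.4.2). An overall ranking of the cohorts cannot be drawn.
- The all-ambulatory count already contains gastroenterology outpatient visits. The information is diluted, not absent. For confounding to remain, gastroenterology contact would have to predict both vaccination and HZ given everything else, and no figure in the documents shows that.
- Differing covariate lists are not a fault in themselves. The disease cohorts are analysed separately, and no objective compares VE between diseases.
- Section 7.6 leaves propensity-score details to the SAP, which is not shown and could add the variable without contradicting the protocol.

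All of this limits what can be claimed, but it does not remove the omission. Section 6.3 sets out a disease-specific list that skips one primary cohort without giving a reason. Exact medication matching is also fairly coarse for IBD: Category 3 pools biologics, methotrexate and thiopurines, whereas the RA scheme separates conventional drugs from biologics. A specialist count could still carry information within that category.

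**Conclusion.** The point holds for the specialist-visit component alone. IBD is the only one of six primary cohorts with no such count in Section 6.3, and followed as written, the IBD propensity model and balance check lack a disease-specific form of a proxy on which the plan relies. Residual confounding of the IBD VE may be larger as a result; that it is larger is not established.

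Neither direction nor size can be derived from the documents. If vaccinated patients have more specialist contact and that contact marks higher HZ risk, VE would be understated; with the reverse imbalance, it would be overstated. The illustrated shift of 4 to 7% in the hazard ratio, or 0.3 to 0.5 SE, rests on an assumed standardized difference of 0.2, an assumed HR of 1.5 to 2 and no help from correlated covariates. For those inputs it leans towards the high side. This is a worthwhile but modest improvement and does not threaten the primary objective.

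**What to change.** Add to the medical-encounters item of Section 6.3 a count of gastroenterologist outpatient visits over the 365-day baseline, for IBD (UC and CD). Enter it in the IBD propensity models for the two-dose and one-dose cohorts, and include it in the IBD balance table so that the imbalance rule of Section 7.6 applies to it. If it was left out on purpose, for example because specialty coding is incomplete, state the reason in the protocol.

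The cost is one more variable derived from provider specialty codes, which the other specialist counts already require. The documents do not report how complete specialty coding is, so that should be checked first. No sample-size figure changes.

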## 11.3.6. Missing data

Missing data will be handled differently depending on the data. For demographic variables, the rate of missing data is <5% and so it's negligible. For healthcare cost level, a cost of zero will be considered if a vaccinated participant does not have any cost reported in the baseline period (such participants will be matched with unvaccinated participants with no cost reported, so missing data would not impact the analysis). For the other variables, these are based on ICD codes and the variables will be defined as Y/N format. Handling missing data using more complex methods is being reviewed. More details of the approaches to address missing data will be included in the SAP.

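### The negative-cost rule in Section 6.3 blanks valid comparator costs, and the zero-cost rationale in Section 11.3.6 relies on a cost match that Section 7.6 does not perform

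*Protocol*

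**What the plan says.** Section 6.3 lists healthcare cost level, in percentile categories over the 365 days before index, among the covariates. It fixes two cleaning rules:

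- **Zero cost.** "Participants followed during the observation period without any claims reported" receive a cost of $0.
- **Negative cost.** A participant's negative estimated cost is set to missing, and "the cost of all the unvaccinated matched participants will be set to missing also".

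Section 11.3.6 gives the zero-cost rule again in different terms: "a cost of zero will be considered if a vaccinated participant does not have any cost reported in the baseline period". It defends the rule on the ground that "such participants will be matched with unvaccinated participants with no cost reported, so missing data would not impact the analysis".

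Section 7.6 describes the matching in two stages. Vaccinated participants are first "matched exactly with unvaccinated participants on age category by 5-year increments" and on AID-related medication category, within the same AID. A logistic propensity model then uses "independent variables as outlined in Section 6.2 to select the 3 unvaccinated participants which are the closest to each vaccinated participant". Section 6.2 refers the reader to Section 6.3 for the covariate list. Matching is with replacement.

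**The concern.** A negative annual total is a fault in one person's record. The rule spreads it to other people whose costs are sound, and the protocol gives no reason for doing so. The variable affected is one that decides who the comparators are, so the order in which cost is cleaned and matches are formed matters, and the protocol leaves that order unclear.

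The zero-cost passage raises a separate difficulty. Its statement that missing data do no harm depends on matched people agreeing on absent cost, which the matching section does not provide for. At stake are a cleaning rule that two programmers could implement differently, an avoidable loss of confounder information, and a missing-data statement in the protocol that its own design does not support.

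**Working it through.** The plan gives no figure for this rule, so there is nothing to reproduce. The check sets the sections side by side and then gives a sense of scale.

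**1. Is cost in the propensity model?** Yes. Section 7.6 takes its independent variables from Section 6.2, Section 6.2 points to Section 6.3, and Section 6.3 lists healthcare cost level.

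**2. Which match does the negative-cost rule mean?** Sections 1.3 and 7.6 both put an exact match before the propensity score, so *matched* can be read in more than one way.

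- *Reading A, the final 1:3 set.* The set is formed by the propensity score, the score uses cost, and the rule changes cost according to the set. The rule cannot be run before matching. With replacement, a comparator who serves two vaccinees may have cost blanked through one match and kept through the other.
- *Reading B, the age-by-medication pool.* The pool exists before the score is fitted, so there is no loop. One negative cost then blanks every comparator in that cell.
- *Applied only once matching is complete.* There is no loop, but valid values disappear before the balance check and before any Cox adjustment for covariates left imbalanced.

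**3. Scale.** Let *f* be the share of vaccinated participants with a negative cost. The protocol does not give *f*; the values below are assumptions. N is the two-dose count in Table 3 (RA 15,928; SLE 2,910).

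Reading A, comparator rows blanked = 3 × N × *f*:

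| *f* | RA | SLE |
|---|---|---|
| 0.1% | 3 × 15,928 × 0.001 = 48 | 3 × 2,910 × 0.001 = 9 |
| 1% | 478 | 87 |
| 2% | 956 | 175 |

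These are maxima in rows. With replacement, the number of distinct people is smaller.

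Reading B, share of cells with at least one negative cost = 1 − (1 − *f*)^(N / cells), assuming an even spread:

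- RA: 7 age groups × 5 medication categories = 35 cells, and 15,928 / 35 = 455 vaccinees per cell. The share is 20% at *f* = 0.05%, 37% at 0.1% and 99% at 1%. With the 81,639 unvaccinated RA participants of Table 2 spread evenly, each affected cell holds about 81,639 / 35 = 2,333 comparators.
- SLE: 7 × 4 = 28 cells (assuming the three listed medication categories plus none), and 2,910 / 28 = 104 per cell. The share is 10% at 0.1% and 65% at 1%.

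**4. Does the zero-cost rationale follow from the matching?** The exact-match factors in Section 7.6 are age category and medication category within AID. Cost enters only through the propensity score, and two people with nearly the same score can differ on any single covariate. Agreement on absent cost is therefore not assured.

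**5. Are the two zero-cost rules the same?** No.

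| | Section 6.3 | Section 11.3.6 |
|---|---|---|
| Trigger | no claims | no cost reported |
| Who | any participant | vaccinated participants |
| Period named | observation period | baseline period |

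The AID algorithms in Section 7.5 almost always require claims in the 365-day baseline (the SLE rheumatologist route states no window). An eligible person with truly no baseline claims should thus be very rare. Someone with claims but no reported cost more plausibly has an unrecorded cost than a cost of $0. That last step is inference: the protocol gives neither the frequency nor the cause of absent costs.

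**The case against.** The strongest reply has three parts.

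*The order of operations is defensible.* Section 7.6 performs an exact match first, so a matched set does exist before the propensity model. This stands: a reader might infer that the rule is circular however it is read, and the text does not support that. The loop arises under Reading A only. Reading B removes the loop but blanks many more valid costs.

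*The rest belongs to the SAP.* Section 6.3 defers the definition of cost level, and Section 11.3.6 says that more complex missing-data methods are under review. This stands for how a missing cost is handled later. A reader might infer that blanked participants, or whole matched sets, drop out of the analysis. That assumes complete-case logistic regression, which the protocol does not state, and a categorised cost variable can carry a missing level. The deferral does not reach the blanking rule, the zero rule or the matching rationale, because the protocol states these itself.

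*Cost is one covariate among many.* Age and medication are matched exactly. Encounters, comorbidities, vaccinations and preventive services remain in the score. Covariates still imbalanced enter the Cox model. This also stands, and it limits the likely effect on VE. A reader might further infer that the plan relies on cost to represent disease severity. Section 5.2.1 names medication use and healthcare use as its proxies, and Section 6.3 lists cost separately from encounters, so that reading lacks direct support.

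**Conclusion.** The point holds in a limited form. The negative-cost rule removes valid data from people whose records are not at fault. It is either dependent on its own result or very wide in reach, according to which match is meant. The no-impact statement in Section 11.3.6 rests on a cost match that the design does not make, and its zero-cost trigger conflicts with that of Section 6.3.

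The size is unknown, because the protocol gives no frequency of negative or absent costs; the counts above rest on assumed values of *f* and, for Reading B, on evenly filled cells. No bias in VE is shown, and under the 1:3 reading it is probably small if negative costs are rare. The comparators affected are those matched to a participant with a negative cost, not all comparators in the study. A $0 cost for a continuously enrolled person with truly no claims is a valid value and is not criticised. The correction is worth making because it is cheap and removes an ambiguity from the matching.

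**What to change.** In Section 6.3, derive and clean cost for each person separately, at that person's index date, before the propensity model is fitted, with the same rule for vaccinated and unvaccinated participants:

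- A negative cost, or no cost recorded despite baseline claims, places only that person in an *unknown* level of the categorised cost variable.
- $0 is kept for people with truly no claims in the baseline period.
- Comparators keep their own valid costs; the clause that blanks them is deleted.

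In Section 11.3.6, restate the zero-cost rule in the same terms as Section 6.3, and delete the statement that zero-cost participants are matched to comparators without a reported cost, together with the no-impact conclusion drawn from it.

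The change costs a few sentences in two sections and trivial programming. No participant is lost and the design is unchanged. Reporting how many people in each group fall in the *unknown* level would show whether the matter has any practical weight.
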